6.0 SCHEDULE OF ASSESSMENT AND PROCEDURES

For screening, treatment period and follow-up procedures, see Schedule of Assessments.

For the treatment period discussed below, where multiple procedures are scheduled at the same nominal time point(s) relative to dosing, the following prioritization of events should be adhered to, where possible, in order of the most important to the least important:

- Clinical safety lab tests – obtain prior to study drug administration.
- Blood pressure/ pulse rate – may be obtained prior to or after ECG collection but must be obtained prior to study drug administration.
- ECGs – obtain within 30 minutes of drug administration.
- Other procedures – All other procedures should be obtained as close as possible to the scheduled time, but may be obtained before or after blood specimen collection, unless sampling is determined by the study personnel to potentially impact the results.

6.1 Screening Period

All patients will be screened and screening procedures performed within 28 days prior to the start of induction treatment.

The required screening assessments and laboratory tests are summarized in the [Schedule of Assessments](#) and [Section 7.0 Assessments](#). Following completion of the screening assessments and confirmation of eligibility, patients may be initiate study treatment.

6.2 Study Treatment Period

Treatment will continue until progression of disease (PD) or unacceptable toxicity, withdrawal of consent by the patient, or non-compliance by the patient with protocol

requirements. Safety assessments will be performed as illustrated in the Schedule of Assessments.

Per the physician's discretion, a patient may continue treatment even if there is progression of disease after avelumab is added as long as the patient remains clinically stable and/or pseudoprogression is assumed.

Clinical and radiological examinations for disease status are performed every 2 cycles or 8 weeks (\pm 7 days) for up to 1 year. After completion of 1 year, tumor assessments will be performed every 3 cycles or 12 weeks (\pm 7 days) during treatment, independent of cycle delays.

If a patient discontinues treatment due to any other reason than disease progression/ death/ withdrawal of informed consent, the disease evaluations shall continue until disease progression. This includes patients who wish to discontinue treatment, but agree that further data is captured for the purpose of the study (partial withdrawal).

6.3 End of Treatment Visit

Patients that discontinue from treatment will undergo an end of treatment (EOT) visit, regardless of the reason of discontinuation, 30 days (+/-7 days) after the last dose of study medication.

In the event a patient is unable to return to the clinic for the follow-up visit, telephone contact with the patient to assess adverse events and concomitant medications and treatment is expected. If laboratory assessments are needed to follow-up unresolved adverse events, retrieval of assessments performed at an institution local to the patient is acceptable.

6.4 Follow-Up Phase

Patients who discontinue treatment for reasons other than progression of disease (and withdrawal of consent for participation in the trial) will continue to visit the clinic for evaluation of their disease by CT/MRI scan approximately every 12 weeks until

progression of disease is determined or patient receives additional anti-neoplastic medication.

Of note, a patient may decide to discontinue study treatment. This is not the same as full withdrawal of consent to participate in the trial and these patients should be encouraged to continue to be followed up as for other patients until progression of disease. If a patient chooses to have no further interaction regarding the study (fully withdrawal of consent), the investigator must provide written documentation of the patient's decision to fully withdraw from the study.

Investigators will collect survival data for patients after progression of disease unless patient fully withdrew consent to participate in the study by using information from a chart review, patient visit, or telephone call. The telephone call will be less than five minutes to obtain information regarding survival status.

6.5 Patient Withdrawal

Patients will be free to discontinue treatment or withdraw from the study at any time, for any reason, or they may be withdrawn/ removed if necessary in order to protect their health (see reasons for withdrawal below). It is understood by all concerned that an excessive rate of withdrawals can render the study uninterpretable; therefore, unnecessary withdrawal of subjects should be avoided. Patients who are withdrawn from the study outside of the DLT period will not be replaced.

Patients will be removed from further treatment for the following reasons:

- Disease progression;
- Non-compliance;
- Need of treatment with medications not allowed by the study protocol;
- Patient no longer consents to participate in the study;
- Intercurrent illness that interferes with study assessments;
- Incidence or severity of AEs in this study indicates a potential health hazard to the patient;
- Investigator discretion;

- Pregnancy;
- Termination of the study.

Reasons for withdrawal from study follow-up may include:

- Completed study follow-up;
- Study terminated by Sponsor;
- Lost to follow-up;
- Refusal for further follow-up for survival;
- Death.

If there is a medical reason for withdrawal of treatment, the patient will remain under the supervision of the investigator until the AEs have been resolved or declined to baseline values.

If a patient has failed to attend scheduled assessments in the study, the investigator must determine the reasons and circumstances as completely and accurately as possible.

In case of premature discontinuation of the study treatment, the investigations scheduled for the EOT and the follow-up visits should be performed, if possible. The reason for discontinuation has to be documented in the eCRF in all cases. Should a patient decide to withdraw, every effort will be made to complete and report the observations as thoroughly as possible. The investigator should contact the patient to determine as completely as possible the reason for the withdrawal. A complete final evaluation at the time of the patient's withdrawal should be made, with an explanation of why the patient is withdrawing from the study. If the reason for removal of a patient from the study is an adverse event or an abnormal laboratory test result, the principal specific event or test will be recorded on the case report form.

If a patient withdraws consent for further study treatment, the patient should still be followed for progression and survival. If a patient withdraws consent for further participation in the study, follow-up assessments will be discontinued.

7.0 ASSESSMENTS

Every effort should be made to ensure that the protocol required tests and procedures are completed as described. However, it is anticipated that from time to time there may be circumstances, outside of the control of the investigator, which may make it unfeasible to perform the test. In these cases, the investigator will take all steps necessary to ensure the safety and well-being of the patient. When a protocol required test cannot be performed the investigator will document the reason for this and any corrective and preventive actions which he/she has taken to ensure that normal processes are adhered to as soon as possible. The study team will be informed of these incidents in a timely fashion.

All procedures should be followed within the allowed flexibility windows as outlined in the Schedule of Assessments.

7.1 Safety Assessments

Safety assessments will include collection of AEs, SAEs, vital signs and physical examination, ECG (12 lead), laboratory assessments, including pregnancy tests and verification of concurrent medications.

7.1.1 Pregnancy Testing

For female patients of childbearing potential, a serum or urine pregnancy test, with sensitivity of at least 25 mIU/mL, will be performed on 2 occasions prior to starting study therapy-once at the start of screening and once at the baseline visit (prior to initiating study drugs (Arms A-C) or radiation (Arm D), immediately before investigational product administration.

Following a negative pregnancy result at screening, appropriate contraception must be commenced and a further negative pregnancy result will then be required at the baseline visit before the patient may receive the investigational product. Pregnancy tests will also be routinely repeated at every cycle during the active treatment period, at the end of study therapy, and additionally whenever 1 menstrual cycle is missed or when potential pregnancy is otherwise suspected. In the case of a positive hCG test

and confirmed pregnancy, the patient will be withdrawn from the study medication and will be withdrawn from the study. Additional pregnancy tests may also be undertaken if requested by Institutional Review Board (IRB)/ Independent Ethics Committee (IECs) or if required by local regulations.

7.1.2 Adverse Events

An adverse event (AE) is the appearance or worsening of any undesirable sign, symptom, or medical condition occurring after starting the study drug even if the event is not considered to be related to study drug. Medical conditions/diseases present before starting study drug are only considered adverse events if they worsen after starting study drug. Abnormal laboratory values or test results constitute adverse events only if they induce clinical signs or symptoms, are considered clinically significant, or require therapy.

Assessment of AEs will include the type, incidence, severity (graded by the National Cancer Institute Common Terminology Criteria for Adverse Events [NCI CTCAE] version 4.03) timing, seriousness, and relatedness.

AEs that occur during the study, including baseline signs and symptoms, will be recorded on the AEs CRF page. The active reporting period begins from the time that the patient provides informed consent, which is obtained prior to the patient's participation in the study, ie, prior to undergoing any study-related procedure and/or receiving investigational product, through and including 30 calendar days after the last administration of the investigational product.

The investigator (or physician designee) is responsible for verifying and providing source documentation for all adverse events and assigning the attribution for all adverse events for subjects enrolled.

Table 11: Recommended Adverse Event Recording Guidelines

Recommended Adverse Event Recording Guidelines

Attribution	Grade 1	Grade 2	Grade 3	Grade 4	Grade 5
-------------	---------	---------	---------	---------	---------

Unrelated	Phase I	Phase I	Phase I	Phase I	Phase I
			Phase II	Phase II	Phase II
				Phase III	Phase III
Unlikely	Phase I	Phase I	Phase I	Phase I	Phase I
			Phase II	Phase II	Phase II
				Phase III	Phase III
Possible	Phase I	Phase I	Phase I	Phase I	Phase I
	Phase II	Phase II	Phase II	Phase II	Phase II
		Phase III	Phase III	Phase III	Phase III
Probable	Phase I	Phase I	Phase I	Phase I	Phase I
	Phase II	Phase II	Phase II	Phase II	Phase II
		Phase III	Phase III	Phase III	Phase III
Definitive	Phase I	Phase I	Phase I	Phase I	Phase I
	Phase II	Phase II	Phase II	Phase II	Phase II
		Phase III	Phase III	Phase III	Phase III

7.1.3 Laboratory Safety Assessments

Hematology, serum chemistry, and thyroid function labs will be drawn at the time points described in the Schedule of Assessments and analyzed at local laboratories. All laboratory safety assessments conducted on Cycle 1 Day 1 (C1D1) for Arms A-C or prior to radiation for Arm D must be completed prior to dosing; hematology and chemistry results must be reviewed by an advance practice provider or a physician prior to dosing.

Assessments performed on dosing days in each subsequent cycle should be performed within 48 hours prior to dosing. Investigators may have additional blood tests performed for the purpose of planning treatment administration, dose modification, or following AEs.

For Arms A-C, there is no need to repeat C1D1 laboratory assessments if baseline assessment is performed within 2 days prior to that date. For Arm D, there is no need to repeat initial laboratory assessments if baseline assessment is performed within 3 days prior to initiation of radiation.

Hematology	Chemistry	Endocrine Monitoring	Coagulation	Urinalysis	Pregnancy Test	Hepatitis Screening	Cardiac Enzyme Monitoring
Hemoglobin	ALT	TSH	PT or INR	Urine dipstick for urine protein: If positive($\geq 2+$), collect 24-hr urine or collect spot urine) and microscopic (Reflex Testing)	For female patients of childbearing potential, serum or urine	Hepatitis B surface antigen and core antibody; anti-hepatitis C antibody.	Troponin T and NT-proBNP
Platelets	AST	Free T4	PTT				
WBC	Alkaline Phosphatase	Total T3					
Absolute Neutrophils	Sodium						
	Potassium						
Absolute Monocytes	Magnesium			Urine dipstick for urine blood: If positive and clinically indicated collect a microscopic (Reflex Testing)			
Absolute Eosinophils	Chloride						
Absolute Basophils	Total Calcium						
	Total Bilirubin Direct Bilirubin Indirect Bilirubin						
	Blood urea nitrogen (BUN) or Urea						
	Creatinine						
	Uric Acid						
	Glucose (non-fasted)						
	Albumin						

Hematology	Chemistry	Endocrine Monitoring	Coagulation	Urinalysis	Pregnancy Test	Hepatitis Screening	Cardiac Enzyme Monitoring
	Phosphorous or Phosphate						
	Total protein						
	Amylase						
	Lipase						
	Creatine kinase						
	Lactate dehydrogenase (LDH)						
	Bicarbonate						

7.1.4 Vital Signs and Physical Examination

Patients will have a physical exam to include weight, vital signs, assessment of ECOG status and height.

A complete physical examination (PE) will be performed at Screening, Days 1 and 15 of each cycle, and the End of Treatment visit for each patient and will include the measurement of body weight, vital signs and assessment of ECOG performance status. Findings of all physical examinations should be recorded in the source documents, and any change from baseline considered by the investigator to be clinically significant should be recorded as an adverse event in the CRF. At screening only, height will be obtained from the electronic medical record.

Abbreviated PEs should be performed as appropriate at each visit where complete physical exams are not required, with special attention to skin and mucosa, and on an as needed basis for assessment of adverse events. Abbreviated exams should be targeted to specific symptoms or complaints and be consistent with local standard of care.

Patient's body weight will be measured at Day 1 of each dosing cycle, and it will be used to calculate the patient's dose of study treatment for that cycle.

Vital signs will include measurements of blood pressure, pulse rate and temperature (oral, tympanic, temporal or axillary). Sitting blood pressure (BP) will be measured with the patient's arm supported at the level of the heart and recorded to the nearest mmHg after approximately 5 minutes of rest. On Day 1 of each cycle, vital signs should be measured prior to infusion start (pre-dose) of first study drug (if more than one study drug is given) and 1 hour after the start of the infusion of last study drug (if more than one study drug is given). The same arm (preferably the dominant arm) will be used throughout the trial. The blood pressure cuff, which has been properly sized and calibrated, should be used to measure blood pressure. The use of automated devices for measuring BP and pulse rate is acceptable.

7.1.5 ECG Assessments

Electrocardiogram (ECG): Single 12-lead (with a 10-second rhythm strip) tracing in the supine position will be used for all ECGs. It is preferable that the machine used has a capacity to calculate the standard intervals automatically. Single ECGs will be performed Day 1 of every cycle.

If the QTc is prolonged (>500 msec by any correction method, ie, CTCAE Grade 3), then the ECG should be re-evaluated by a qualified person at the site for confirmation as soon as the finding is made, including verification that the machine reading is accurate. If manual reading verifies a QTcF of >500 msec, immediate correction for reversible causes (including electrolyte abnormalities, hypoxia and concomitant medications for drugs with the potential to prolong the QTc interval) should be performed. In addition, repeat ECG should be immediately performed hourly for at least 3 hours until the QTc interval resolves to Grade 1 or less.

If QTc interval reverts to less than 500 msec, and in the judgment of Investigator(s) and the MDACC IND Office is determined to be due to cause(s) other than study drug, treatment may be continued with regular ECG monitoring. If in that timeframe the QTc intervals rise above 500 msec the study drug will be held until the QTc interval decreases to Grade 1 or less. Patients will then re-start the study drug at the next lowest dose level. If the QTc interval has still not decreased to <500 msec after 2 weeks, or if at any time a patient has a QTc interval >515 msec or becomes symptomatic, the patient will be removed from the study. Additional triplicate ECGs may be performed as clinically indicated.

Prior to concluding that an episode of prolongation of the QTc interval is due to study drug, thorough consideration should be given to potential precipitating factors (eg, change in patient clinical condition, effect of concurrent medication, electrolyte disturbance) and possible evaluation by specialist.

If patient experiences a cardiac or neurologic AE (specifically syncope, dizziness, seizures, or stroke), an ECG (triplicate) should be obtained at the time of the event.

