3.2.1 Arm A: Avelumab + Utomilumab (4-1BB)

In Arm A of avelumab and utomilumab, there will be no dose escalation. The escalation of avelumab and utomilumab will be performed under a previously conducted Pfizer protocol.

The Arm A MTD expansion will enroll up to 14 patients at the established safe dose for additional safety and correlative studies to establish the RP2D for this combination.

Utomilumab will be administered at the fixed flat dose of 100 milligrams (mg) intravenously (IV) on Day 1 of each 28-day cycle or every 4 weeks. Avelumab will be administered at the fixed dose of 10 mg/kg IV on Day 15 of Cycle 1 and Days 1 and Day 15 of subsequent cycles. Premedications will be administered per institutional standard.

On days when both avelumab and utomilumab are administered, avelumab will be administered first.

Patients will be restaged at the end of every two cycles and tumor response evaluation will be based on Response Evaluation Criteria in Solid Tumors (RECIST) 1.1 and immune-related RECIST (irRECIST). Patients may be allowed to continue treatment

after two cycles of avelumab combinations if there is continued clinical response or disease stabilization and patients do not have significant toxicities. A patient may continue treatment on this combination therapy until the patient experiences confirmed disease progression, unacceptable adverse event(s), intercurrent illness that prevents further administration of treatment, and/or treatment is discontinued following investigator's decision to withdraw the patient, pregnancy, patient withdraws consent, noncompliance with trial treatment or procedure requirements, or administrative reasons.

Table 3: Dosing for Arm A: Avelumab + Utomilumab (4-1BB)

Dose Level	Utomilumab (4-1BB) IV Every 4 Weeks Starting Cycle 1 Day 1	Avelumab IV Every 2 Weeks Starting Cycle 1 Day 15
MTD/RP2D Determined by Pfizer	100 mg	10 mg/kg

As of Amendment Version 06, the avelumab dosing for Arm A was revised; therefore, a new cohort of 14 patients was enrolled.

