Dose Level	Radiation Days -5 to -1	Utomilumab (4-1BB) IV Every 4 Weeks Starting Cycle 1 Day 1	Avelumab IV Every 2 Weeks Starting Cycle 1 Day 15
1 (Start)	24 Gy in 8 Gy / fraction for 3 fractions	100 mg	10 mg/kg
-1	21 Gy in 7 Gy/ fraction for 3 fractions	100 mg	10 mg/kg

As of Amendment Version 09, the avelumab and radiation dosing for Arm D was revised; therefore, the dose de-escalation was re-started.

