5.2.4.3 Dose Modifications

In the event that a DLT that is at least possibly related to one of the study drugs occurs, patients will halt treatment with study drugs until symptoms resolve to the grade outlined in [Section 5.2.4.2](#), and then treatment can be restarted. After the first two cycles reduction in the frequency of dosing in study drug(s) may be required based on the worst toxicity experienced in the previous cycle.

No specific dose adjustments are recommended for Grade 1/2 treatment-related toxicity. However, investigators should always manage their patients according to their medical judgment based on the particular clinical circumstances.

During dose escalation cohorts, patients experiencing recurrent and intolerable Grade 2 toxicity may resume dosing at the next lower dose level or at a decreased frequency once recovery to $>/=\text{Grade 1}$ or baseline is achieved. Patients enrolled in the expansion cohorts may resume dosing, once recovery to $</=\text{Grade 1}$ or baseline is achieved after experiencing recurrent and intolerable $>/=\text{Grade 2}$. If a dose or frequency reduction is required due to the treatment related toxicity, this may be allowed as an alternative to discontinuation of treatment, upon agreement with the MDACC IND Office.

Once a patient has a dose reduction or reduction in the frequency in the dosing for a drug-related toxicity, the dose will not be re-escalated. Patient requiring more than two dose reductions will be withdrawn from treatment unless otherwise agreed between the investigator and the MDACC IND Office.

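### Section 7.1.5 orders a restart one dose level down after a QTc hold, but Tables 3 to 6 define no lower drug level in any arm

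*Combined protocol and SAP*

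**What the plan says.** Section 7.1.5 sets out a sequence. A QTc above 500 msec, which the section classes as CTCAE Grade 3, is verified and reversible causes are corrected. If QTc falls back below 500 msec and the event is attributed to something other than study drug, treatment may go on with monitoring. If QTc then rises above 500 msec again, "the study drug will be held until the QTc interval decreases to Grade 1 or less". The next sentence reads: "Patients will then re-start the study drug at the next lowest dose level". Patients are instead removed from the study if QTc exceeds 515 msec at any time, if they become symptomatic, or if QTc is still not below 500 msec after 2 weeks.

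Section 5.2.4.3 deals with toxicity in general. After recurrent, intolerable Grade 2 toxicity, patients in dose escalation cohorts "may resume dosing at the next lower dose level or at a decreased frequency". For the rest, "Patients enrolled in the expansion cohorts may resume dosing" after recovery, with no level named. Of a dose or frequency reduction for treatment-related toxicity it says that "this may be allowed as an alternative to discontinuation of treatment, upon agreement with the MDACC IND Office". It also sets a ceiling, "Patient requiring more than two dose reductions will be withdrawn from treatment", unless the investigator and the IND Office agree otherwise. Table 8, in the same section, requires the immunotherapy agents to be discontinued for any Grade 3 adverse drug reaction outside a list of exceptions.

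The doses are in Sections 3.2.1 to 3.2.4. Tables 3, 4 and 5 each have a single row, labelled "MTD/RP2D Determined by Pfizer". Table 6 has level 1 and level -1; the radiation entry for level -1 is "21 Gy in 7 Gy/ fraction for 3 fractions".

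**The concern.** An instruction to step down a dose level works only if there is a level to step down to. The restart in Section 7.1.5 is directive, offers no other route, and does not say which of the two or three drugs in a combination is lowered. A site that has just held drug for a cardiac finding the protocol calls Grade 3 would have to restart at the same dose, choose a dose the protocol does not give, or deviate. That is chiefly a safety matter. There is also a smaller data matter: Sections 9.3 and 9.6.1 summarise toxicity by dose level, and a patient restarted under this rule would belong to no defined level.

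**Working it through.** There is no plan figure to reproduce. The check is a count of dose levels, followed by a comparison of the sections.

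**1. Drug levels per arm (Tables 3 to 6).**

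| Arm | Utomilumab | PF-04518600 | Avelumab | Lower drug level |
|---|---|---|---|---|
| A (Table 3) | 100 mg | not given | 10 mg/kg | 0 |
| B (Table 4) | not given | 0.3 mg/kg | 10 mg/kg | 0 |
| C (Table 5) | 20 mg | 0.3 mg/kg | 10 mg/kg | 0 |
| D, level 1 (Table 6) | 100 mg | not given | 10 mg/kg | 0 |
| D, level -1 (Table 6) | 100 mg | not given | 10 mg/kg | 0 |

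The drug-by-arm combinations number 2 + 2 + 3 + 2 = 9. Each has exactly one dose, so 0 of 9 have a lower level, and 0 of 4 arms do.

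**2. What Arm D level -1 changes.** Radiation goes from 3 × 8 = 24 Gy to 3 × 7 = 21 Gy, a fall of 3 Gy (3/24 = 12.5%). Utomilumab changes by 100 − 100 = 0 mg and avelumab by 10 − 10 = 0 mg/kg. Section 3.2.4 has radiation completed in the lead-in, before Cycle 1 Day 1. Moving a patient from level 1 to level -1 during treatment therefore alters no dose still to be given.

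**3. Lower drug doses elsewhere.** Section 5.2.3.3 says PF-04518600 with utomilumab starts at 0.1 mg/kg and rises to 0.3 mg/kg. Only Arm C combines those two drugs. Section 3.2.3 says Arm C has no escalation as of Amendment Version 05 and gives one PF-04518600 dose, 0.3 mg/kg. If the 0.1 mg/kg step were nevertheless counted, a lower level would exist for 1 of 9 drug-by-arm combinations and 1 of 4 arms. Utomilumab and avelumab would still have none.

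**4. Section 5.2.4.3.** Its lower-level option applies to dose escalation cohorts. Section 3.1 enrols Arms A to C in expansion cohorts only, so among current cohorts the option reaches Arm D, whose first part Section 3.2.4 calls a dose escalation phase. By step 2, the lower level there does not lower either drug. The section counts dose reductions but defines no steps.

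**5. Table 8 against Section 7.1.5.** Section 7.1.5 treats QTc above 500 msec as Grade 3 and provides for restart. Table 8 requires discontinuation for Grade 3 adverse drug reactions; its exceptions cover transient flu-like symptoms or fever, certain transient symptoms, single laboratory values, tumor flare and performance status. QTc is not named. For an event judged drug-related, one section provides for restart and the other for stopping.

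**The case against.** The strongest reply is that the protocol does offer ways to reduce exposure. Section 5.2.4.3 is permissive, allows a decreased frequency as an alternative to a lower level, and allows a dose or frequency reduction with IND Office agreement. That stands. A reader might infer that no toxicity-driven reduction can be carried out anywhere in the trial; the documents do not support it. The gap lies in the Section 7.1.5 restart and in the dose-level branch of Section 5.2.4.3 for Arm D.

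A reader might also infer that the withdrawal ceiling of more than two reductions presupposes two tabulated lower levels. It does not. It is a ceiling, qualified by agreement with the IND Office, in a section that allows reductions by such agreement. The steps are undefined, which is not the same as impossible.

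The QTc trigger is narrow. It concerns a renewed rise above 500 msec in patients who stay at or below 515 msec, remain asymptomatic and are not removed at 2 weeks. The documents give no expected frequency.

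Finally, a reader might infer that the by-dose-level toxicity summary or the RP2D evidence is corrupted. Nothing in the documents supports an effect of that size. The MTD rests on DLTs in the first 56 days, and Section 5.2.4.2 requires each dose modification and its reason to be recorded in the eCRF, so the exposure actually given should be recoverable.

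None of this rescues the sentence in Section 7.1.5, which contains neither the frequency option nor the IND Office route for the restart.

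**Conclusion.** The Section 7.1.5 restart instruction is wrong as written. It is an internal inconsistency: a directive safety rule that, when followed, leads to no defined drug dose in any of the four arms and in Arm D would leave every remaining dose unchanged. Two related inconsistencies belong with it: the 0.1 mg/kg PF-04518600 step in Section 5.2.3.3 against Section 3.2.3, and the Grade 3 discontinuation rule in Table 8 against the restart.

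The conclusion assumes that a dose level means a row of Tables 3 to 6, where that term heads the first column. The Table 8 conflict further assumes that the QTc event is judged an adverse drug reaction; Section 7.1.5 does not state the attribution of the second rise. How many patients would be affected cannot be estimated from the documents, and any effect on the dose-level summaries is secondary.

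**What to change.** The sponsor should reconcile Section 7.1.5 with Tables 3 to 6 (Sections 3.2.1 to 3.2.4), Section 5.2.3.3, Section 5.2.4.3 and Table 8, so that:

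- the QTc restart names the drug or drugs concerned and refers to an action the protocol defines;
- the lower-level option and the count of reductions in Section 5.2.4.3 refer to defined steps, or are worded so as not to need them;
- Sections 5.2.3.3 and 3.2.3 agree on the PF-04518600 levels in Arm C;
- Section 7.1.5 and Table 8 agree on what follows a Grade 3 QTc event.

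Which dose, action or rule applies is for the sponsor to decide; none is proposed here. The cost is amendment wording in these sections and, if the sponsor so chooses, in the dose tables. Reconciling the text requires no added patients or procedures.
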